6.1 INCLUSION CRITERIA

- 1. Subject is male or female and 18 to 80 years old (inclusive) at time of enrollment (signing of consent).
- 2. Subject has significant venous reflux by DUS, defined as reverse flow with reflux duration greater than 0.5 seconds after the Valsalva maneuver or distal augmentation while the patient is standing or in reverse Trendelenburg position.
- 3. Subject is eligible for endovascular treatment, as determined by the treating investigator.
- 4. Subject's general physical condition allows for a significant amount of ambulation after the procedure, as determined by the treating investigator.
- 5. Subject is willing and able to complete study requirements, including all follow-up visits and assessments.
- 6. Subject voluntarily provides written informed consent to participate in this study.

6.2 EXCLUSION CRITERIA

- 1. There is evidence of old or fresh thrombus in the subject's diseased vein segment to be treated, as determined by DUS within 2 weeks prior to the index procedure.
- 2. In the judgment of the treating investigator heat energy delivery to the subject would be contraindicated.
- 3. Subject is concurrently participating in another interventional clinical trial.
- 4. Subject is pregnant or plans to be pregnant or lactating at the time of the treatment procedure.
- 5. Subject has known or suspected allergies or contraindications to any general or local anesthetic agents and/or any antibiotic medication that cannot be adequately pre-treated.

7 PRE-SURGICAL ASSESSMENT (Baseline Study Visit)

Potential subjects will be examined by the Investigator or his/her designee and evaluated according to the inclusion/exclusion criteria for participation in this study. Demographics, medical history (including previous venous interventions, risk factors/co-morbidities, and

Document Title: EU Post Market Clinical Follow-Up Study of the Venclose System for Saphenous Vein Incompetence

concomitant conditions/medications), and a venous Duplex Ultrasound will be performed during pre-surgical assessment, and the results recorded on the *Baseline Case Report Form*.

7.1 INFORMED CONSENT

For subjects who potentially meet study eligibility criteria, study participation will be carefully explained. Subjects who choose to continue in the evaluation will be asked to read the *Study Informed Consent Form* and will be given the opportunity to review the information and ask questions.

It is the responsibility of the treating physician or his/her designee to obtain voluntary written informed consent (according to local legal requirements and regulations). The information is intended to give each participant a thorough understanding of the purpose and nature of the PMCF study, the study requirements and visit commitments, and the potential benefits and risks of the study treatment. As part of the informed consent process, the investigator is instructed to inform the patient that he/she is free to refuse participation or to withdraw from the study at any time, without consequence. The patient is to understand that participation in the study is not required in order to receive treatment with the CE-marked Venclose System, and that alternative treatments (e.g., treatment with another endovenous ablation system or alternative method such as foam sclerotherapy) are available for venous insufficiency. A consent form in a language understood by the patient will be made available. The signed informed consent is retained in the patient's medical file(s) along with documentation of the informed consent conversation and process by the person who obtained consent. A copy of the informed consent will be provided to the patient. Signing of the Study Informed Consent Form formally enters the subject as a study participant and indicates the participant's willingness to comply with the pre-procedure, treatment, and follow-up study requirements. If participants withdraw from the study prior to treatment with the treatment device, additional patient(s) may be enrolled in order to achieve a total of 25 treated patients.

7.2 BASELINE STUDY ASSESSMENTS, CHRONIC VENOUS INSUFFICIENCY QUALITY OF LIFE QUESTIONNAIRE (CIVIQ-20)

Once the subject has agreed to participate in the study and signed the Study Informed Consent Form, the investigator will perform an assessment using the Clinical Etiologic Anatomic Pathophysiologic (CEAP) Classification and the Venous Clinical Severity Score (VCSS).

The subject will complete a self-administered questionnaire called the Chronic Venous Insufficiency Quality of Life Questionnaire (CIVIQ-20). The questionnaire assesses quality of life for patients with chronic venous disease using 20 questions in which the patient rates symptoms on a scale from 1 (no pain) to 5 (severe pain).

Document Title: EU Post Market Clinical Follow-Up Study of the Venclose System for Saphenous Vein Incompetence

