Participant	Twelve months post-procedure
Duration	
Study Site(s)	One study site located in Germany
Sample Size	Up to 25 subjects treated with the Venclose System
	Baseline Visit Treatment Visit Follow-Un Visits (3-day 3-month 6-
Study Visits	month and 1 year post procedure)
	month, and T year post procedure)
	1. Vein Occlusion Rate (percentage of limbs with occlusion of the treated
	vein) at 3-day, 3-month, 6-month, and 12-month Follow-up Visits.
Primary	
Endpoints	2. Reflux-free Rate (percentage of limbs without reflux, as determined by
	Duplex Ultrasound Scan) at 3-day, 3-month, 6-month, and 12-month
	Follow-up Visits.
Secondary	Clinical signs and symptoms of lower limb venous disease at baseline 2
Endnointe	months 6 months and 12 months as measured by
Enupoints	monuis, o monuis, and 12 monuis as measured by:

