5 STUDY ENDPOINTS

5.1 PRIMARY ENDPOINTS

The primary study endpoints are percentage of limbs with vein occlusion in the treated vein and the absence of reflux in the treated vein, as determined by Duplex Ultrasound Scan (DUS).

Primary endpoint analysis will be accomplished by measuring the treated vein recanalization and reflux rates at 3 days (+/- 2 days), 3-months (+/- 2 weeks), 6 months (+/- 3 weeks) and 12 months (+/- 4 weeks) post-procedure. Recanalization will be determined by DUS and clinical assessment during follow-up. A twelve-month follow-up is sufficient to assess a stable occlusion in the treated vein, as it is the typical final follow-up time frame for varicose vein treatment when assessing technical and symptomatic recurrence.

Specific primary endpoint measurements will be:

 Vein Occlusion Rate – percentage of limbs with occlusion of the treated vein: Occlusion is defined as the absence of any flow from 3 cm inferior to the Saphenofemoral Junction (SFJ) along the entire length of the treated vein as documented on the post-procedure and follow-up DUS. The 3 cm limit was selected

Document Title: EU Post Market Clinical Follow-Up Study of the Venclose System for Saphenous Vein Incompetence

to represent the occlusion status of the proximal Great Saphenous Vein (GSV) and to allow precise evaluation with a typical 4 cm linear ultrasound probe. In line with the equivalent ClosureFast device clinical studies^{2,3} flow in the stump of the GSV up to 3 cm below the SFJ is considered normal and does not constitute a failure.

2) Reflux-Free Rate – percentage of limbs without reflux in the treated vein: Reflux is measured by Duplex Ultrasound imaging along the entire treated vein segment(s). Reflux is defined as reversal flow >0.5 seconds with subject standing or in reverse Trendelenburg position of at least 15° after distal augmentation.

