6 OVERVIEW OF STUDY DESIGN

Potential subjects presenting with signs and symptoms of chronic lower limb venous disease and significant reflux in the GSV will be further screened for study participation and enrollment. All enrolled subjects will meet study eligibility criteria as described in the inclusion and exclusion criteria sections below.

After voluntarily providing informed consent to participate, eligible subjects will undergo a minimally invasive procedure, which involves delivering controlled radiofrequency energy for ablation of the great saphenous vein (GSV). All procedures will be performed by surgeons determined to be experienced with the Venclose System and will take place at a single study site, Venenzentrum am Bruehl, [name]. The study will enroll up to 25 treated subjects. The study site will receive the Venclose System components for the treatment of study patients, free of charge.

After the treatment procedure, subjects will be evaluated four (4) times to determine the incidence of adverse events, and to assess vein recanalization and reflux. Follow-up visits occur at 3 days (+/-2 days), 3-months (+/- 2 weeks), 6 months (+/- 3 weeks) and 12 months (+/- 4 weeks) post-procedure. Each follow-up visit will consist of a clinical examination,

⁶ Vasquez et al., Revision of the venous clinical severity score: venous outcomes consensus statement: special communication of the American Venous Forum Ad Hoc Outcomes Working Group. *J Vasc Surg.* 2010 Nov;52(5):1387-1396.

Document Title: EU Post Market Clinical Follow-Up Study of the Venclose System for Saphenous Vein Incompetence

CIVIQ-20 Patient Questionnaire (except 3-day visit), patient satisfaction survey, and Duplex Ultrasound (DUS) examination of the treated limb in the reverse Trendelenburg position. A supine (rather than standing) position for DUS examinations is preferred in order to allow comparison with vein diameters obtained during the procedure.

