12 DEVICE MALFUNCTIONS

All device malfunctions (a failure of a device to perform in accordance with its intended purpose when used in accordance with the manufacturer's instructions) whether or not the malfunction resulted in an adverse event will be reported to Venclose immediately. Malfunctioning devices are required to be returned to Venclose for analysis following internal Returned Merchandise Authorization Process Procedures. Venclose will attempt to confirm the malfunction/failure and the details of the malfunction will be reviewed per Venclose's Complaint Handling Procedures, which establish the requirements for reporting medical device incidents under the Medical Device Vigilance System.

Document Title: EU Post Market Clinical Follow-Up Study of the Venclose System for Saphenous Vein Incompetence

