APPENDIX 1 - List of Potential Adverse Events

Based on the overall experience reported in the medical literature with endovenous thermal ablation by radiofrequency or laser, the following potential adverse events are provided as a guide:

1. Reaction to Local Anesthesia:

Some people may have hypersensitivity or allergic reaction to certain types of local anesthesia. Prescreening the subject with a small amount of anesthesia can be performed. Venclose defers to physician judgment in selecting the appropriate agent and amount.

2. Deep Vein Thrombosis or Pulmonary Embolism:

Potential for deep vein thrombosis (DVT) exists, usually less than 1 in 100 treated limbs. If a DVT blood clot breaks loose it can travel to the lung and cause pulmonary embolism (PE), usually less than 1 in 10,000 limbs.

3. Allergy to Product Component:

The catheter has undergone biocompatibility testing to ensure safety of the components. Some people may have a hypersensitivity or allergic reaction to one or more of the components.

4. Perforation of the Saphenous Vein:

The saphenous vein may be perforated during advancement of the catheter. Minimal mechanical injury to the soft tissue and hematoma may result.

5. Thermal Skin Injury:

A burn is the partial or complete destruction of skin caused by some form of energy, usually thermal energy.

6. Skin Discoloration or Pigmentation:

Blood degradation in the soft tissues may result in skin discoloration. The majority of these skin changes resolve spontaneously over several months to a year. Some discoloration may be permanent.

Document Title: EU Post Market Clinical Follow-Up Study of the Venclose System for Saphenous Vein Incompetence

7. Infection:

There is always a small chance of infection with any surgical procedure, however, the catheter is sterilized and is meant for one-time use. Aseptic (sterile) technique will be used during the procedure.

8. Neurological Injury:

Motor nerves that could cause partial paralysis are typically avoided in endovenous thermal ablation procedures, and reports of such paralysis are extremely rare at less than 1 in 1,000,000 limbs.

9. Parasthesia:

Parasthesia is defined as abnormal physical sensations such as numbness, prickling or tingling. This usually goes away within a few months, but can be permanent.

10. Superficial Venous Thrombophlebitis:

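### Limbs in which the catheter was introduced but no energy delivered could be classed as untreated, replaced, and left out of both primary rates

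*Combined protocol and SAP*

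**What the plan says.** The sample is counted in treated people throughout. The synopsis gives "Up to 25 subjects treated with the Venclose System" and Section 6 says "The study will enroll up to 25 treated subjects". Section 7.1 makes consent the point of entry ("Signing of the Study Informed Consent Form formally enters the subject as a study participant") and then provides for replacement: "If participants withdraw from the study prior to treatment with the treatment device, additional patient(s) may be enrolled". The stated aim of that provision is that 25 people end up treated.

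The first primary endpoint in Section 5.1 is the "percentage of limbs with occlusion of the treated vein". The second is the reflux-free rate, also confined to the treated vein.

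The protocol has no formal definition of treatment. Section 3 uses the word for a single energy cycle, delivered once the catheter is in place. Section 15 names no analysis population. Its rule for early exits covers only subjects who have already been treated. It undertakes to report adjunctive procedures, adverse events and deviations, but not failed attempts or malfunctions.

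The protocol does foresee trouble around the procedure. Appendix 1, item 4 notes that "The saphenous vein may be perforated during advancement of the catheter". Section 12 requires every malfunction, defined as "a failure of a device to perform in accordance with its intended purpose" under correct use, to be reported to the sponsor.

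**The concern.** The study exists to confirm safety and performance (Section 2), and its results feed the clinical evaluation of a marketed device (Section 16). Getting the catheter into position and delivering energy is part of performance. If a limb enters the primary rates only once energy has been delivered, those rates are conditional on the procedure having worked up to that point. If an untreated subject also uses none of the 25 places, recruitment simply continues until 25 have been treated.

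Any such exclusion acts in one direction: it can only raise the occlusion and reflux-free rates relative to all limbs attempted. With about 25 subjects, a single limb is visible in the result.

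**Working it through.** **Reading the text.** The gap follows in four steps.

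1. The 25 are treated subjects (synopsis, Sections 6 and 7.1), so an attempted but untreated subject takes no place, whatever the exit is called.
2. Read as in Section 3, treatment means energy delivery, so a failed advancement, or a catheter that will not start, comes before treatment.
3. A limb that received no energy has no treated vein, and Section 5.1 gives it no value on either primary endpoint.
4. Section 15 provides no attempted-limb denominator and no technical-success rate through which it could re-enter.

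**Sample size.** The figure of 25 cannot be reproduced, because the protocol gives no alpha, power, expected rate, margin or dropout. It is not challenged here. What follows is a sensitivity calculation only.

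**Inputs.** There are 25 treated subjects (protocol). One limb per subject is assumed. The number of attempted limbs that received no energy, *k*, is not in the protocol and is assumed to be 1 or 2.

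**Formulas.** With *x* successes, the treated-limb rate is *x*/25 and the attempted-limb rate is *x*/(25 + *k*). The exact (Clopper-Pearson) 95% limits for *x*/*n* are the 2.5% point of Beta(*x*, *n* − *x* + 1) and the 97.5% point of Beta(*x* + 1, *n* − *x*). When *x* = *n* the upper limit is 100% and the lower is 0.025^(1/*n*), so for 25/25 it is 0.025^(1/25) = 86.3%.

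| Successes | Treated limbs only | *k* = 1 | *k* = 2 |
|---|---|---|---|
| 25 | 25/25 = 100% (86.3 to 100) | 25/26 = 96.2% (80.4 to 99.9) | 25/27 = 92.6% (75.7 to 99.1) |
| 24 | 24/25 = 96.0% (79.6 to 99.9) | 24/26 = 92.3% (74.9 to 99.1) | 24/27 = 88.9% (70.8 to 97.6) |

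Each omitted limb is worth between 3 and 4 percentage points.

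**How likely is at least one?** If each attempt fails before energy delivery with probability *q*, the chance of at least one such failure before 25 are treated is 1 − (1 − *q*)^25. The expected number replaced is 25*q*/(1 − *q*). All values of *q* are assumptions.

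| *q* | Chance of at least one | Expected number replaced |
|---|---|---|
| 1% | 22% | 0.25 |
| 2% | 40% | 0.51 |
| 5% | 72% | 1.32 |
| 10% | 93% | 2.78 |

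**Bilateral treatment.** Section 7.3 allows both limbs to be treated and analysed separately. More limbs dilute the effect of one omission. At the extreme of 50 treated limbs (25 × 2), one omitted failure moves 50/50 = 100% to 50/51 = 98.0%.

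**The case against.** The strongest reply is that the replacement clause concerns participants who withdraw. It sits in the consent section, shortly after the reminder that patients may leave freely. Section 14 distinguishes withdrawal of consent from termination by the investigator or sponsor, and nowhere is a failed attempt called a withdrawal. This stands. A reader might infer that the protocol contains a rule for swapping out failed procedures; it does not. The gap comes from terms left undefined. It survives the reply because the sample is counted in treated subjects even without the replacement clause.

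A reader might also infer that device failures in general escape the rate. They do not. A vein that received energy and was not occluded, recanalized or refluxed is a treated vein and counts as a failure at each ultrasound visit. Nor do the passages on perforation and malfunction show that either event leads to an abandoned procedure. Appendix 1 mentions only minor tissue injury and hematoma, and Section 12 is general.

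Nor would such cases be concealed. Procedure details and adverse events go on case report forms (Section 8), malfunctions go to the sponsor (Section 12), and each enrolled subject has an exit form (Section 14). They would be documented, but outside the performance rates.

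Finally, scoring every failed attempt as not occluded would mix technical success with durability of closure. That is a fair criticism of replacing the treated-limb rate, and the reason to report both rates side by side.

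**Conclusion.** The concern holds in a limited form. The protocol leaves room for a limb with a failed attempt before energy delivery to be classed as untreated and omitted from both primary rates while recruitment continues to 25 treated. Nothing in it prevents this, and the effect would be upward. Failures during or after energy delivery are not affected, except that a partly treated vein is judged only over the length that was treated.

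The size is illustrative: between 3 and 4 points per omitted limb, resting on one limb per subject and an assumed one or two failed attempts. The true number could be zero, in which case the two rates coincide. Because the protocol sets no success threshold or margin, no stated decision would be reversed. What is at stake is how the reported rate is read. This is an inexpensive improvement that should be made, not a flaw that invalidates the study.

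**What to change.** - **Section 7.1:** allow replacement only for subjects who leave before the Venclose catheter is introduced.
- **Sections 5.1 and 15:** state when treatment starts. Report the occlusion and reflux-free rates for all limbs in which catheter introduction was attempted, counting limbs that received no energy as failures, beside the rates for treated limbs. Score partly treated limbs by duplex ultrasound and show them separately.
- **Section 15:** add a technical-success rate, and a list of every subject enrolled but not treated, with the reason.
- **Treatment Visit CRF:** make sure it records the outcome of each attempt. The form is not among the documents, and the Device Usage Log in Section 19 is specified to hold only subject ID, catheter lot number and date of use, so it cannot be assumed that this outcome is already captured.

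The cost is a few sentences and possibly one form field, with no new procedures. The downside is that the attempted-limb rate may be slightly lower than the treated-limb rate.

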7.3 SUBJECT CONFIDENTIALITY AND IDENTIFICATION

All information concerning subjects or their participation in this study will be considered confidential. Only authorized Venclose personnel and designated consultants and regulatory agencies (in the event of a regulatory audit) will have access to these confidential files. The investigator and designated study personnel will assign a unique identifier that will be used to maintain confidentiality of subjects' medical information. Subject's full names or initials and other protected health information (PHI) will not be captured on the case report forms, except patient self-reported questionnaires/surveys. For patient self-reported questionnaires/surveys. For patient self-reported questionnaires or venclose representatives. In addition, any images or reports submitted from the participating site to Venclose or Venclose representatives will be redacted of all subject identifiers.

Subjects' identifying information will be recorded on a Master Enrollment Log with access restricted to the Investigator and designated study personnel.

On all source documents, case report forms, and any other documents provided to the Sponsor, the following subject identification coding for enrolled subjects will be used:

$\underline{EXAMPLES}$ $\underline{V 1 \cdot 0 1 \cdot J 0 N A D}$ $\underline{V 1 \cdot 0 2 \cdot M I L S T}$ $\underline{V 1 \cdot 0 3 \cdot S T U J E}$

Document Title: EU Post Market Clinical Follow-Up Study of the Venclose System for Saphenous Vein Incompetence

Note: Data for patients treated in bilateral limbs may be analyzed on a per-patient or perlimb basis, as appropriate. Patients treated in bilateral limbs will be counted as one subject for data analyzed per-patient (and for the purposes of adverse event data). For data analyzed per-limb, the two limbs will be analyzed separately.

Subjects will be given a date for surgery(s) during the Pre-Surgical Assessment (Baseline Visit) (with 14 allowable days between baseline assessments and the procedure).

8 SURGICAL PROCEDURE

In accordance with routine clinical commercial practice, study investigators will receive in-service training by Venclose personnel or its representatives for the use of the Venclose System as well as product labeling and training materials, which include the Venclose digiRF User Manual (LB00003) (generator) and Venclose Catheter IFU (LB00002).

The surgical procedure with the Venclose System will be conducted in accordance with the EU approved Venclose Catheter IFU and the Venclose digiRF User Manual (generator). The typical training program for the commercial device includes information about supplies, patient preparation, vein access, skin marking and measurement, device preparation, insertion, placement and local anesthetic, energy delivery and post-surgery recovery. Training that is specific to the performance of the study includes documentation requirements and procedures for the timely transmission of data. Procedure details and adverse events assessment will be recorded on the *Treatment Visit Case Report Form and Adverse Event Case Report Form*.

The Venclose procedure will be performed on the GSV per standard of care. For the GSV, no other treatment modalities are allowed (i.e. no phlebectomy or sclerotherapy).

Adjunctive procedures for treatment of side branches (i.e. anterior accessory saphenous vein) may be performed per standard of care including phlebectomy and sclerotherapy.

